## 6.5 POOLING OF CENTRES

This section is not applicable because the trial is performed in only one centre.

## 6.6 HANDLING OF MISSING DATA AND OUTLIERS

Data of screened subjects who were withdrawn from the trial prior to first administration of any study drug will not be reported in the CTR.

Data of subjects who failed to complete all periods of the study (dropouts or withdrawals) will be reported in the CTR as far as their data are available. All withdrawals will be documented and the reason for withdrawal reported in the CTR.

**CTP Section 7.5.1:** *It is not planned to impute missing values for safety parameters.*

One exception where imputation might be necessary for safety evaluation are AE dates. Missing or incomplete AE dates are imputed according to BI standards [\(3\)](#).

No imputation will be done for ECG endpoints. If replicate ECG recordings are missing, the arithmetic means per time point will be computed with the reduced (1 or 2) number of recordings. If single cardiac cycles (also denoted as beats or waveforms) are missing, the arithmetic mean per single ECG will be computed with the reduced (1, 2 or 3) number of cardiac cycles.

Missing data and outliers of PK data are handled according to BI standards [\(4\)](#) and [\(5\)](#).

**CTP Section 7.5.2:** *PK parameters that cannot be reasonably calculated based on the available drug concentration-time data will not be imputed.*

## 6.7 BASELINE, TIME WINDOWS AND CALCULATED VISITS

A separate baseline is defined for each treatment period: Baseline is the last available off-treatment value before administration of the respective treatment (BI, BI fasted, BI fed). Off-treatment in this context means that a value measured within an on-treatment phase, as defined in [Table 6.1: 1](#), will not be used as baseline for any study treatment.

There will be a centralised evaluation of 12-lead ECG recordings at the time points specified in [Table 6.7: 1](#).

Three triplicate ECGs will be recorded as the baseline before the each oral drug administration, but only all 3 single ECGs of the first of the 3 triplicates will be transferred to the database. Triple ECGs (3 single ECGs recorded within 180 sec) will be recorded on all on-treatment time points with centralised ECG evaluation.

The baseline value of an ECG variable is defined as the mean of the triple ECG measurements prior to first study drug administration. For all on-treatment assessments, only the first of the three replicate ECG at a single assessment time will be centrally evaluated.

Table 6.7: 1 Time schedule of 12-lead ECG recordings with centralised evaluation

Visit	Day	Planned time [hh:mm] - relative to respective drug administration	Study phase
2/3/4	1	-01:00	Baseline On-treatment
		01:00	
		04:00	
		08:00 	
		12:00	
	2	24:00	

 in Part 1 only

For the exposure response analyses, pairs of ECG variables and corresponding plasma concentrations will be built using the same planned time points, e.g., the HR change from baseline and the plasma concentration measured at planned time 01:00 will build one pair. Whether a time deviation between PK blood sampling time and corresponding ECG recording is too big for a reliable assessment and the pair has to be excluded from the analysis will be decided no later than at the RPM.

Time windows are defined in Section 6.1 of the CTP. Adherence to time windows will be checked at the RPM.

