			5:15	13:15	Stop of IV infusion containing [C-14]-BI 1358894	x	x					
			5:30	13:30		x	x					
			5:45	13:45		x	x					
			6:00	14:00	240 mL fluid intake, thereafter lunch ³	x	x			x		
			6:30	14:30		x	x					
			7:00	15:00		x	x					
			8:00	16:00		x	x		x ⁸	x		
			10:00	18:00	Dinner ³	x	x		x ⁸	x		
			12:00	20:00		x	x		x ⁸	x		
	2		24:00	08:00	Breakfast ³	x ¹³	x	x	x ⁸	x		
			34:00	18:00		x	x			x		
	3		48:00	08:00	Breakfast ³	x	x		x	x		
	4		72:00	08:00	Breakfast ³	x	x			x		
	5		96:00	08:00	Breakfast (voluntary) ³ , Discharge from trial site ¹⁰	x	x	x	x	x		
	7		144:00	08:00	Ambulatory visit	x	x	x			x	
	9		192:00	08:00	Ambulatory visit	x	x				x	
	11		240:00	08:00	Ambulatory visit	x	x	x			x	
	14		312:00	08:00	Ambulatory visit	x	x	x			x	

Proprietary confidential information © 2020 Boehringer Ingelheim International GmbH or one or more of its affiliated companies

1. Subject must be informed and written informed consent obtained prior to starting any screening procedures. Screening procedures include physical examination, check of vital signs, ECG, safety laboratory (including drug screening, urine alcohol test, hepatitis serology and HIV antibodies), demographics (including determination of body height and weight, smoking status and alcohol history), relevant medical history, concomitant therapy and review of inclusion/exclusion criteria, neurological examination and suicidality assessment (C-SSRS).
2. The time is approximate; the procedure is to be performed and completed within the 2 h prior to drug administration.
3. If several actions are indicated at the same time, the intake of meals will be the last action.
4. Safety laboratory including urine drug screening and urine alcohol test will be done at this time point.
5. AEs and concomitant therapies will be recorded throughout the trial, but will be specifically asked for twice daily during in-house days.
6. Prior to BI drug administration 3 triplicate ECGs will be recorded within approximately one hour. The recordings should be separated by at least 15 minutes.
7. Sampling times and periods may be adapted based on information obtained during the trial (e.g. preliminary PK data) including addition of samples and visits as long as the total blood volume taken does not exceed 500 mL per subject.
8. ECGs taken at these time points should be performed as triplicate and will be sent out for external evaluation.

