5.2.4 Electrocardiogram

Recording and storing

Twelve-lead ECGs (I, II, III, aVR, aVL, aVF, V1 - V6) will be recorded using a computerised electrocardiograph (e.g. Mortara Eli 250 C) at the times provided in the [Flow Chart](#).

To achieve a stable heart rate at rest and to assure high quality recordings, the site personnel will be instructed to assure a relaxed and quiet environment, so that all subjects are at complete rest.

All ECGs will be recorded for a 10 sec duration after subjects have rested for at least 5 min in a supine position. ECG assessment will always precede all other study procedures scheduled for the same time to avoid compromising ECG quality.

ECGs will be recorded as single ECGs or as triplicate ECGs (i.e. three single ECGs recorded within 180 sec) as indicated in the [Flow Chart](#).

All ECGs will be stored electronically. Electrode placement will be performed according to the method of Wilson, Goldberger and Einthoven.

All locally printed ECGs will be evaluated by the investigator or a designee. Abnormal findings will be reported as AEs (during the trial) or baseline conditions (at screening) if assessed to be clinically relevant by the investigator. Any ECG abnormalities will be carefully monitored and, if necessary, the subject will be removed from the trial and will receive the appropriate medical treatment.

ECGs may be repeated for quality reasons (for instance, due to alternating current artefacts, muscle movements, or electrode dislocation) and the repeated ECG will be used for analysis. Additional (unscheduled) ECGs may be collected by the investigator for safety reasons.

Data transfer

In case of repeat ECGs due to quality reasons, all recordings will be transferred to the central ECG lab and the repeated ECGs will be flagged in the database.

Unscheduled ECGs (for safety reasons) will be transferred to the central ECG lab and evaluated but will not be included into the statistical analysis of interval lengths. Data transfer from the central ECG lab to the sponsor is described in the ECG data transfer agreement (see TMF).

Evaluation by the central ECG laboratory

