Central ECG lab evaluation will be performed for the first of three replicate ECGs per time point with ECG recordings as specified in the [Flow Chart](#) (i.e., Day 1 up to 24 h post-dose for each Period). The remaining second and third replicate ECGs will be stored for additional analyses, if required, e.g. by authorities at a later time point. For baseline, where 3 triplicate ECGs are recorded, only the first of the triplicate ECGs (i.e. 3 single ECGs) will be evaluated.

Central evaluation will include the determination of cardiac QRS-axis as assessed by the ECG machine's algorithm as well as the intervals RR, PR, QRS and QT measured semi-automatically. The remaining second and third replicate ECG will be stored for additional analysis if required, e.g. by authorities at a later time point.

Heart rate (HR) and the QT interval corrected for HR (QTc e.g. QTcF and QTcB) will be determined by the sponsor (see TSAP for details). All semi-automatic interval measurements in one subject will be performed on the same lead. The intervals will be measured from four cardiac cycles (beats) in lead II. If lead II shows a flat T wave or is not measurable for any reason, lead V5 will be used, or if that lead is not measurable, then lead I will be used. The lead actually used will be reported in the CTR.

For automatic interval measurements no lead will be provided. After quality control, the fiducial point markings will be reviewed by the cardiologist assigned to the study. For blinding arrangements see Section [4.1.5](#). No more than two blinded readers will evaluate all ECGs of the study. ECGs from a particular subject should be evaluated by single reader.

For quality assurance and control of measurements, all ECGs of a subject will be subsequently reviewed by the ECG technician supervisor or his/ her designee to assess the overall variance of the measured intervals and, to detect accidental switching of leads and/or false subject assignments of the ECGs. After quality control, the fiducial point markings will be reviewed by the cardiologist assigned to the study.

Evaluation of ECGs will comply with the ICH E14 guidance document and supplements [\[R07-4722\]](#), [\[R16-0366\]](#) as well as the FDA requirements for annotated digital ECGs [\[R09-4830\]](#).

Evaluation by Trial site

All local ECGs will be evaluated by the investigator or a designee.

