#### **7.8.4 ECG**

Abnormal findings will be reported as baseline conditions (prior to first study drug administration) or as AEs (from first study drug administration onwards) if judged clinically relevant by the investigator.

The ECG exposure response analysis will be based on the ECGPCS. All other descriptive analysis of ECG endpoints will be based on the TS.

Generally, ECG measurements will not be included in the statistical analysis if one of the following applies:

- No date or time available for ECG measurement
- Pre-dose measurement done after first drug administration
- On-treatment measurement done before first drug administration
- Measurement is a repeated measurement
- More than 3 single ECGs (i.e., measurements from 4th single ECG onwards will not be included)
- Unscheduled measurements

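### SAP 6.7 and 7.8.4 tie the ECG baseline to the first study drug administration, which read literally leaves Part 2 without its own pre-dose baseline

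*SAP*

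**What the plan says.** Protocol flow charts, both parts: "Prior to BI drug administration 3 triplicate ECGs will be recorded within approximately one hour", and "The recordings should be separated by at least 15 minutes". The SAP repeats this for each period: "Three triplicate ECGs will be recorded as the baseline before the each oral drug administration" (6.7). Of these, "only all 3 single ECGs of the first of the 3 triplicates will be transferred to the database".

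On which value serves as baseline, SAP 6.7 gives two rules:

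- A general rule at the start of the section: each treatment period has its own baseline, the last off-treatment value before the respective treatment. Table 6.7: 1 fits this, with a baseline at -01:00 for Visits 2/3/4, timed relative to the respective administration.
- An ECG rule further down: "The baseline value of an ECG variable is defined as the mean of the triple ECG measurements prior to first study drug administration".

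SAP 7.8.4 then lists ECG measurements to be left out of the statistical analysis. One item is "Pre-dose measurement done after first drug administration". The next is its mirror image, for on-treatment ECGs taken before the first administration.

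**The concern.** The trial has three oral dosing occasions per subject, and all of Part 2 comes after the first study drug administration of the trial. If *first* is read across the whole trial, the ECG sentence in 6.7 fixes one baseline, in Period 1, for all periods. The rule in 7.8.4 then removes the Period 2 and 3 pre-dose ECGs that would have served instead.

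Every Part 2 change from baseline in QTcF, HR, QT, PR and QRS depends on this. So do the exposure-response pairs for QTcF and HR, and any notable-finding flag that is based on change. The QTcF scatterplot carries a reference line at 60 msec, and a point's position relative to that line moves one for one with its baseline.

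**Working it through.** **1. What the literal rules remove.** Inputs: 12 subjects and three oral doses each (Protocol 3.3, 6.2.2); one triplicate of 3 single ECGs per pre-dose occasion (SAP 6.7); post-dose time points in Table 6.7: 1 of 1, 4, 8 (Part 1 only), 12 and 24 h.

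- Pre-dose sets: 12 × 3 = 36. Removed: 12 × 2 = 24, or 24 × 3 = 72 single ECGs.
- Post-dose changes: 12 × (5 + 4 + 4) = 156. In Part 2: 12 × (4 + 4) = 96.

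**2. Age of the remaining baseline.** Doses are at least 17 days apart (Protocol 3.1). The Period 1 baseline is therefore at least 17 days old at the Period 2 dose and at least 17 + 17 = 34 days old at the Period 3 dose.

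**3. Would a Period 2 or 3 pre-dose ECG qualify under the general rule?** It must lie outside any on-treatment phase (SAP Table 6.1: 1).

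- The Part 1 phase ends 11 × 24 = 264 h after the end of infusion. The infusion ends 5.25 h after the tablet, so the phase ends 269.25 h after the tablet.
- The Period 2 pre-dose ECG falls within 2 h before a dose given at least 17 × 24 = 408 h after the tablet, hence at 406 h or later.
- In Part 2 the phase ends 264 h after the dose, again well before 406 h.

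The per-period baseline is available and off-treatment. Nothing in the design calls for a Period 1 baseline in Part 2.

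**4. Which sense of *first* does the SAP use?** The opening of 7.8.4 separates baseline conditions from AEs at the first study drug administration, and 7.2 uses the same phrase for concomitant medication. Both are most naturally read across the whole trial. A programmer would have reason to carry that sense into the exclusion list a few lines later. In that sense the mirror rule is also too loose: it could never catch a Period 2 or 3 ECG labelled on-treatment but recorded before that period's dose.

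**5. Size of the noise effect.** The documents state no ECG variance, so there is no plan figure to reproduce. Assumptions: the within-day variance of a single read is scaled to 1; a share ρ of it lies between recordings minutes apart; independent day-to-day variance is κ (range 0 to 1). On-treatment values are single reads (SAP 6.7).

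- Variance of one triplicate mean: A = ρ + (1 − ρ)/3. At ρ = 0.5, A = 0.667.
- Change from a same-day baseline: 1 + A = 1.667.
- Change from a Period 1 baseline: 1 + A + 2κ.

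At ρ = 0.5:

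| κ | Variance, Period 1 baseline | SD relative to same-day baseline |
|---|---|---|
| 0 | 1.667 | 1.00 |
| 0.25 | 2.167 | √(2.167/1.667) = 1.14 |
| 0.5 | 2.667 | √(2.667/1.667) = 1.26 |
| 1 | 3.667 | √(3.667/1.667) = 1.48 |

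At κ = 1 the ratio is √(3.5/1.5) = 1.53 for ρ = 0.25 and √(3.833/1.833) = 1.45 for ρ = 0.75. These figures apply to the 1, 4 and 12 h values. The 24 h value is on Day 2 and carries the day-to-day term under either baseline. Apart from noise, any shift in a subject's level between Part 1 and Part 2 would enter the Part 2 mean changes in full.

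**The case against.** The best defence is that *first* means first within the period. Part 1 has two administrations, a tablet and an infusion five hours later, so the word may only separate the two. The general rule, the sentence on recording before each oral dose, Table 6.7: 1 and the by-treatment ECG analysis in SAP 6.1 all point to a baseline per period. This stands as evidence of intent. A reader might infer that the sponsor plans a single Period 1 baseline; the documents do not support that.

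Intent does not settle what gets programmed, however. The two ECG-specific sentences contradict the general rule, and the more specific rule normally governs. The ECG text also contains wording foreign to this design: 7.8.4 asks for plots by renal function group, which this trial does not have. The wording therefore cannot be assumed to have been fitted to a three-period trial.

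A reader might also infer that using one triplicate is itself a fault, and that one ECG from each of the three triplicates should be averaged instead. That does not hold, for three reasons:

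- Protocol 5.2.4 says "only the first of the triplicate ECGs (i.e. 3 single ECGs) will be evaluated" and describes a triplicate as "three single ECGs recorded within 180 sec". The first triplicate is a permitted reading, so no departure from the protocol is shown.
- Under the model above, the baseline variance ratio (spread reads to one triplicate) is 1/(1 + 2ρ). The fall in the SD of change runs from 0% at ρ = 0 to 1 − √(1.333/2) = 18.4% at ρ = 1. Nothing in the documents places ρ in that range.
- The model treats the three times as interchangeable. In Part 2 the pre-dose ECG is nominally at -1:00, and the breakfast, for T2 only, is at -0:30. Triplicates 15 minutes apart from -1:00 would fall at -1:00, -0:45 and -0:30, so the third could meet the meal in the fed arm only. The 2 h window allows an earlier start but does not require it. Spreading the reads could exchange random noise for a treatment-dependent shift.

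**Conclusion.** The wording is wrong as it stands, though probably not as intended. Two stated rules, applied literally, remove 24 of 36 pre-dose ECG sets and give 96 of 156 scheduled changes a baseline at least 17 or 34 days old. These counts follow from the documents, assuming 12 subjects complete all periods. The loss of precision does not: it runs from 0% to about 53% in the SD of a Day 1 change, over κ from 0 to 1 and ρ from 0.25 to 0.75, all assumed.

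The reach is limited to descriptive ECG tables, flags based on change, and exposure-response plots. No hypothesis test is planned on safety data, and no primary or secondary PK endpoint is affected. The choice of the first triplicate can stay.

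**What to change.** - SAP 6.7: define the ECG baseline as the mean of the triple ECG *prior to the oral drug administration of the respective period*.
- SAP 7.8.4: in both the pre-dose and the on-treatment exclusion rules, replace *first drug administration* with *oral drug administration of the same period*. Naming the oral dose matters because no set of three triplicates is scheduled before the infusion.

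The cost is a text edit and, if programs already exist, a check of the baseline derivation and exclusion flags for Visits 3 and 4. No new recordings, central reads or transfers are needed, because the SAP already has the first triplicate transferred before each oral dose.

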## 7. PLANNED ANALYSIS

The format of the listings and tables will follow the BI guideline "Standards for Reporting of clinical trials and project summaries" ([6](#)).

The individual values of all subjects will be listed. Listings will be sorted by treatment sequence ("Tab/C14-fasted-fed" and "Tab/C14-fed-fasted"), subject number and visit (if visit is applicable in the respective listing). AE listings will be sorted by assigned treatment (see [Section 7.8.1](#) below for details). The listings will be contained in Appendix 16.2 (SDL) of the CTR.

The following standard descriptive statistical parameters will be displayed in summary tables of continuous variables:

N	number of non-missing observations
Mean	arithmetic mean
SD	standard deviation
Min	minimum
Median	median
Max	maximum

For plasma concentrations as well as for all PK parameters the following descriptive statistics will additionally be calculated:

CV	arithmetic coefficient of variation
gMean	geometric mean
gCV	geometric coefficient of variation

For PK parameters the following descriptive statistics will additionally be calculated:

P10	10 th percentile
Q1	1 st quartile
Q3	3 rd quartile
P90	90 th percentile

The data format for descriptive statistics of plasma concentrations will be identical with the data format of the respective concentrations. The descriptive statistics of PK parameters will be calculated using the individual values with the number of decimal places as provided by the evaluation program. Then the individual values as well as the descriptive statistics will be reported with three significant digits in the CTR.

Tabulations of frequencies for categorical data will include all possible categories and will display the number of observations in a category as well as the percentage (%) relative to the respective treatment group. Percentages will be rounded to one decimal place. The category missing will be displayed if and only if there actually are missing values. Percentages will be based on all subjects in the respective subject set whether they have non-missing values or not.

## **7.1 DEMOGRAPHIC AND OTHER BASELINE CHARACTERISTICS**

Only descriptive statistics are planned for this section of the CTR.

## **7.2 CONCOMITANT DISEASES AND MEDICATION**

Concomitant diseases will be coded according to the most recent version of MedDRA. Concomitant medication will be coded according to the most recent version of the World Health Organisation – Drug Dictionary. Concomitant non-drug therapies will be coded according to the most recent version of MedDRA.

A medication will be considered concomitant, if it

- is ongoing at the time of first study drug administration, or
- starts within the analysis phase of the respective treatment (see [Section 6.1](#) for a definition of treatments and analysis phases).

The relevance of the concomitant therapies to the evaluation of PK will be decided no later than at the RPM.

Only descriptive statistics are planned for this section of the CTR.

## **7.3 TREATMENT COMPLIANCE**

Treatment compliance will not be analyzed as a specific endpoint. Any deviations from complete intake will be addressed in the Report Planning Meeting (cf. [Section 6.2](#)) and described in the CTR.

## **7.4 PRIMARY ENDPOINTS**

The analysis of primary endpoints will be based on the PKS.

### **7.4.1 Primary analysis of the primary endpoints**

#### Part 1

The statistical model for the primary endpoint  $AUC_{0-\infty}$  is an analysis of variance (ANOVA) model on the logarithmic scale including “formulation” as fixed effect and “subject” as random effect (cf. CTP Section 7.3.1).

Absolute bioavailability will be estimated by the ratios of the geometric means of  $AUC_{0-\infty}$  for BI 1358894 p.o. (T1) versus  $AUC_{0-\infty}$  for (C-14) BI 1358894 i.v. (R1). The point estimates for the ratios of the geometric means and their two-sided 90% CIs will be provided.

#### Part 2

The statistical model for the primary endpoint  $AUC_{0-312}$  is an ANOVA model on the logarithmic scale including “treatment”, “sequence” and “period” as fixed effects and “subject within sequence” as random effect (cf. CTP Section 7.3.1).

Relative bioavailability will be estimated by the ratios of the geometric means of BI fed (T2) versus BI fasted (R2) of AUC0-312 of BI 1358894. The point estimates for the ratios of the geometric means and their two-sided 90% CIs will be provided.

### Part 1 and 2

